8.2 Secondary objectives

The secondary objectives in this study are:

- To assess drug utilization with Theraflex® for an observation period up to 64 weeks
- To assess patients satisfaction with Theraflex® treatment for an observation period up to 64 weeks
- Description of the use of analgesics for OA for an observation period up to 64 weeks
- Description of patient characteristics (Age, BMI, Weight, Analgesics intake at baseline)

9. Research methods

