9.1.2 Secondary endpoint(s)

The secondary endpoint(s) is/are:

- Drug utilization of Theraflex® therapy as reported by the patient to their physician
- Patient satisfaction measured with a Likert response scale (from 1-very dissatisfied to 5 – very satisfied)
- Type, frequency and length of painkiller for the symptomatic treatment of hip OR knee OA for an observation period up to 64 weeks
- Other medical/physical therapy for OA related pain (drugs/type of therapy, duration of use, dose, frequency)

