9.2.7.2 Visit 1: Enrollment/Initial visit

Visit 1 is the first Visit at the physician after the subject bought the product in a pharmacy and started treatment with Theraflex®. Visit 1 must be within the first 2 weeks after start of treatment with Theraflex®.

A patient who has not been informed about the study prior to the recommendation of Gl+Ch but is currently on Theraflex® treatment within no more than for 2 weeks and meets all inclusion and none of the exclusion criteria can also be included in the study.

During the visit the investigator gives the necessary explanations about the NIS, asks the patient to read the information for the study patients and the informed consent form. If the patient gives the consent to participate in the study, the informed consent is signed both by the patient and the investigator.

During the visit the investigator conducts all examinations according to the local routine clinical practice. In addition the investigator provides to the subject the PRO questionnaire and the overall satisfaction question for completion for Visit 1. If the patient has multiple joint OA or double-sided (bilateral) Knee/Hip OA, only one «target» joint to be selected for the evaluation, where the patient experiences the most severe pain at the time of enrollment. Filling in a questionnaire, the patient needs to associate his/her responses with the "target" joint only during the entire follow-up period.

Following information will be captured in the CRF:

- Date of visit
 - day, month, year
- Date of informed consent
- Radiological Diagnosis of OA of Hip or Knee according to the Kellgren and Lawrence Criteria *
- Patient demographic data
- Gender
- Date of birth
- Race / ethnicity
- Physical Examination
- Weight (kg)
- Height (cm) (V1 only)
- Vital Signs
 - Blood Pressure
 - Body Temperature (axillary temperature)
 - Heart rate
- Lifestyle
- Alcohol and tobacco use
- Review of Theraflex® drug utilization
 - Start / End of treatment
 - Dose/frequency of treatment
- KOOS or HOOS Questionnaire (PRO)
- Patient satisfaction with Theraflex®
- Medical history
- Concomitant disease(s)
- Concomitant medication
- Concomitant non-medication therapies (e.g. physiotherapy, surgery)
- Adverse events

All examinations are performed according to the local routine institutional practice as indicated by the attending physician. PRO should be completed at the time of the visit at the physician by the patient.

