**IMPACT No. 19649 STATISTICAL ANALYSIS PLAN v.2.0 13 JUL 2020**

- Patient satisfaction measured with a Likert response scale (from 1 – very dissatisfied to 5 – very satisfied)
- Type, frequency and length of painkiller for the symptomatic treatment of hip OR knee OA for an observation period
- Other medical/physical therapy for OA related pain (drugs/type of therapy, duration of use, dose, frequency)

4. Study design**4.1. Overall study design and plan**

This is a single country, open-label multicenter non-interventional prospective study.

Figure 4.1:1 Overall Study Design and Plan

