**IMPACT No. 19649 STATISTICAL ANALYSIS PLAN v.2.0 13 JUL 2020**

- Frequency and shift tables based on the results of the scale assessment [*very dissatisfied, dissatisfied, neither satisfied nor dissatisfied, satisfied, very satisfied*] presented overall and separately for patients with knee and hip osteoarthritis;
- Descriptive statistics for results and changes from Visit 1 (as the Likert scale data are best described by the median, not the mean, 95% CI is additionally provided for the median).
- Use of analgesics for symptomatic treatment of osteoarthritis:
 - Data will be presented on the patient's additional analgesic treatment of pain in the target joint (no/occasionally/regularly, topical agents/systemic agents/combined treatment) at the time of starting the chondroprotector (Theraflex/Theraflex Advance), at the time of study completion, as well as the investigator's assessment of the dynamics of the analgesic treatment of pain in the target joint from the start of the chondroprotector (Theraflex/Theraflex Advance) until the patient's discontinuation from the study (not changed/increased/decreased/pain treatment was discontinued) and time until complete cessation of analgesic treatment (1 month/ 2 months/ 3 months/ 6 months/ 12 months after the start of the chondroprotector), if it was completely discontinued;
 - Tables similar to those described in section 8.5 will be presented by pharmacological subgroup (3rd level) and chemical subgroup (4th level) for various indications [Symptomatic treatment with analgesics for target joint OA/ Other medication for target joint OA related pain/ Other therapy for target joint OA];

Individual subject data will be presented in listings.

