**IMPACT No. 19649 STATISTICAL ANALYSIS PLAN v.2.0 13 JUL 2020**

- The percentage of patients with no need for analgesic treatment of pain in the target joint from the start of Theraflex/Theraflex Advance until the end of study participation⁴;
- The percentage of patients with a complete withdrawal of analgesic treatment of pain in the target joint⁵;
- The percentage of patients with no need for surgical intervention/ at the end of observation⁶;
- The percentage of patients with no need for an emergency visit due to persisting joint pain during the study⁷;
- The percentage of patients who required intra-articular⁸ injections of glucocorticosteroids⁹ during the observation period;
- The percentage of patients who required intra-articular injections of hyaluronic acid¹⁰ during the observation period;
- The percentage of patients who required PRP injection therapy¹¹ during the observation period.

Additional KOOS subscale assessment:

- The percentage of patients with a $\geq 20\%$ reduction in pain intensity at Visits 2, 3 and 4 in the group of patients with knee OA as assessed using the relevant KOOS subscale.
- The percentage of patients with a $\geq 20\%$ improvement in symptoms at Visits 2, 3 and 4 in the group of patients with knee OA as assessed using the relevant KOOS subscale.
- The percentage of patients with a $\geq 20\%$ improvement in functional activity at Visits 2, 3 and 4 as assessed using the relevant KOOS subscale in the group of patients with knee OA.
- The percentage of patients with a $\geq 20\%$ improvement in quality of life at Visits 2, 3 and 4 in the group of patients with knee OA as assessed using the relevant KOOS subscale.
- Changes for each KOOS question presented in a shift table.

Additional HOOS subscale assessment:

- The percentage of patients with a $\geq 20\%$ reduction in pain intensity at Visits 2, 3 and 4 in the group of patients with hip OA as assessed using the relevant HOOS subscale.

⁴ According to the “MEDICAL DATA COLLECTION AT THE END OF OBSERVATION” form.

⁵ According to the “MEDICAL DATA COLLECTION AT THE END OF OBSERVATION” form.

⁶ According to the “MEDICAL DATA COLLECTION AT THE END OF OBSERVATION” form.

⁷ According to the “MEDICAL DATA COLLECTION AT THE END OF OBSERVATION” form.

⁸ Route of administration will be provided in the CM domain, CMROUTE = “OTHER” or “intra-articular”.

⁹ A list of glucocorticosteroids will be determined using the CM domain: incomplete ATC code H02AB

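### SAP 9.2 limits the painkiller and other-OA-therapy outputs to the target joint, while Protocol 9.1.2 and SAP 3.2 define these endpoints without that limit

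*SAP*

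**What the plan says.** The secondary objective in Protocol 8.2 is "Description of the use of analgesics for OA for an observation period up to 64 weeks". Protocol 9.1.2 turns this into two endpoints: "Type, frequency and length of painkiller for the symptomatic treatment of hip OR knee OA for an observation period up to 64 weeks", and "Other medical/physical therapy for OA related pain (drugs/type of therapy, duration of use, dose, frequency". The first refers to hip or knee OA and the second names no joint. SAP 3.2 keeps the scope of both, and gives the first as "Type, frequency and length of painkiller for the symptomatic treatment of hip OR knee OA for an observation period".

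The outputs in SAP 9.2 are narrower. The first item reads "Data will be presented on the patient's additional analgesic treatment of pain in the target joint". It covers use at treatment start, use at study completion, the investigator's rating of change, and time to complete cessation. The medication tables that follow are built for three indications: "Symptomatic treatment with analgesics for target joint OA/ Other medication for target joint OA related pain/ Other therapy for target joint OA". Two exploratory percentages in SAP 9.3 have the same limit: patients with no need for analgesics, and "The percentage of patients with a complete withdrawal of analgesic treatment of pain in the target joint".

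The target joint is introduced in Protocol 9.2.7.2. For a patient with multi-joint or bilateral disease, the joint with the worst pain at enrolment is selected for evaluation. The text then continues "Filling in a questionnaire, the patient needs to associate his/her responses with the" target joint alone throughout follow-up.

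**The concern.** The planned outputs answer a narrower question than the endpoint asks, and the SAP gives no reason for the change. Patients with more than one OA joint are expected: Protocol 9.2.7.2 provides for them, and Amendment 1 (Protocol Annex 3) removed the exclusion of patients with both hip and knee OA. For such a patient, a painkiller recorded against the non-target hip or knee meets the endpoint in Protocol 9.1.2 but does not enter the tables in SAP 9.2.

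The study is descriptive and has no comparator, so these percentages are themselves the result. A reader who sees a share of patients using painkillers for OA, or needing none, would take it to cover the patient's OA. It would in fact cover one joint.

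**Working it through.** The documents give no rate of analgesic use and no share of patients with more than one OA joint, so there is no figure to reproduce. The check is a comparison of scope, followed by a bound on direction and an illustration of size.

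**Scope, side by side**

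- Objective (Protocol 8.2): analgesics for OA.
- Painkiller endpoint (Protocol 9.1.2 and 9.3.2, SAP 3.2): hip or knee OA.
- Other-therapy endpoint (same sections): OA-related pain, no joint named.
- SAP 9.2 outputs: all tied to the target joint, under an opening line that speaks of osteoarthritis in general.
- SAP 9.3: two analgesic percentages tied to the target joint. The injection percentages in the same section name no joint.
- Data collected (Protocol 9.3.3.12, SAP 8.5): all concomitant treatment for any indication, with indication and dates recorded for medication.
- SAP 8.5 tables: all prior and concomitant medication by pharmacological and chemical subgroup, not split by OA indication.
- SAP 13: reports no protocol deviations and does not mention the restriction.

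**Direction**

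Let T be the patients with a painkiller recorded for the target joint, and A those with one recorded for OA of any hip or knee. The questionnaires are for hip or knee, so the target joint is one of these and T is contained in A.

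- Any use: share(T) ≤ share(A), so the reported share is equal or lower.
- No need: 1 − share(T) ≥ 1 − share(A), so the reported share is equal or higher.
- Complete withdrawal: not fixed. A patient who stops the target-joint painkiller but continues one for another knee counts as withdrawn under the SAP only. A patient whose only painkiller was for another knee, and who stops it, counts as withdrawn under the wider definition only.
- Rated change: not fixed, for the same reason.

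**Size, by assumption only**

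Let m be the share of patients with more than one OA joint, and q the share of those whose only OA painkiller is recorded for a non-target hip or knee. Neither is in the documents. The shortfall in the share of users is m × q, and on the planned 1100 patients the count is 1100 × m × q.

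- q = 0: no shortfall, whatever m is.
- m = 10%, q = 5%: 0.10 × 0.05 = 0.5 percentage points; 1100 × 0.005 = 5.5, about 6 patients.
- m = 30%, q = 10%: 0.30 × 0.10 = 3.0 points; 33 patients.
- m = 50%, q = 20%: 0.50 × 0.20 = 10.0 points; 110 patients.

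These lines show only how the result depends on m and q. They are not estimates.

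**The case against.** Four points can be made for the plan.

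1. **The medication is still reported.** This stands. SAP 8.5 counts every concomitant drug by subgroup, so a reader might infer that non-target painkillers vanish from the report, and they do not. But the 8.5 tables cannot show which use was for OA. A patient may also appear in several subgroups, so the rows cannot be added up to a number of users. SAP 8.5 is in addition unclear about drugs started before Theraflex and continued: its general sentence and Table 7.2:1 count them as concomitant, while one of its bullets requires a start after the first dose.

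2. **The target joint is a sensible unit.** This stands in part. Protocol 9.2.7.2 selects it for evaluation, and the later visits ask about the outcome of treatment of that joint. Reporting analgesics for the joint that carries the KOOS or HOOS score is defensible. It still needs to be stated, because the endpoint in both documents is wider.

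3. **Investigators may record a systemic painkiller under the target joint anyway.** This stands. The target is by rule the most painful joint, and the CRF indication options are not in the documents. A reader might infer that analgesic use is understated by a definite number of points, or that patients on daily systemic NSAIDs for another knee will be reported as off analgesics. The documents show only that this is possible.

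4. **Some outputs cannot be widened.** This stands. SAP 9.3 takes its two analgesic percentages from the end-of-observation form, and the use and change items in SAP 9.2 read like fixed questions about the target joint. The last visit was planned for February 2020 and the SAP is dated 13 July 2020. Answers about one joint cannot be turned into answers about any joint.

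**Conclusion.** The mismatch is in the text. The SAP 9.2 outputs, and two in SAP 9.3, cover the target joint, while the endpoints cover hip or knee OA (painkillers) and OA-related pain (other therapy). No output gives the endpoint as SAP 3.2 states it, and the restriction is neither explained nor declared.

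The consequence is bounded in direction for two quantities only: the share using OA painkillers is equal to or below the endpoint as defined, and the share with no need is equal or above. A reader might infer that every analgesic result is shifted in the product's favour. That does not follow for complete withdrawal or rated change. The size is unknown and may be near zero. It depends on how many patients have more than one OA joint and how the indication was recorded, and the documents give neither. Patients with a single OA joint are unaffected.

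**What to change.** - In SAP 9.2, add concomitant-medication tables for OA of any hip or knee, and for any OA-related pain in the case of other therapy, as far as the recorded indication allows.
- Add one patient-level line: any systemic analgesic or NSAID for any indication, each patient counted once. State whether drugs started before the first dose and continued are included, since SAP 8.5 is not consistent on this.
- Keep the existing outputs in SAP 9.2 and 9.3, including those from the end-of-observation form, and label each one as target joint only.
- Where the recorded data cannot be widened, say so, and declare the restriction with its reason as a difference from Protocol 9.1.2.

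The cost is SAP wording and a few extra tables, with no new data collection. Reported analgesic use may come out somewhat higher.

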9.3. Exploratory efficacy analysis

In addition to the primary and secondary endpoints specified in the Protocol, this statistical analysis plan provides for an extended analysis. This exploratory analysis will be carried out in the Full Analysis Set (FAS).

List of parameters to be analyzed:

Additional treatment-related analysis:

- The percentage of patients with no progression of arterial hypertension, diabetes mellitus and obesity at the end of observation³

³ According to the “MEDICAL DATA COLLECTION AT THE END OF OBSERVATION” form.
CONFIDENTIAL/PROPRIETARY

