**IMPACT No. 19649 STATISTICAL ANALYSIS PLAN v.2.0 13 JUL 2020**

Data listings will include findings of scheduled and unscheduled visits, repeated examinations and data of prematurely withdrawn subjects.

6. Analysis sets

The following data sets will be included in the analysis:

1. All subjects who signed the informed consent (All screened subjects);
2. Full analysis set (FAS). FAS includes all patients from the All screened subjects population who received at least one dose of Theraflex® with available data for evaluation of at least one efficacy and/or safety parameter after the start of observation period.

7. Statistical assumptions**7.1. Standard descriptive statistics**

All variables will be analysed in an exploratory manner with appropriate descriptive statistical methods: categorical variables by frequency tables (absolute and relative frequencies) and continuous variables by sample statistics (i.e. mean, standard deviation, minimum, median, quartiles and maximum).

Continuous variables will be described by absolute value and as change from baseline per analysis time point, if applicable.

Additionally, measured HOOS/KOOS subscales values and changes from baseline will be presented using 95% CI.

The accuracy of descriptive statistics will be determined according to the following rules:

- mean, median, quartiles: 1 more decimal place than in the raw data;
- standard deviation: 2 more decimal places than in the raw data;
- minimum, maximum: the same number of decimal places as in the raw data;
- percentages: 1 decimal place;
- 95% CI: the same number of decimal places as in the parameter value for which CI is calculated.

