7.2. Missing data

The per protocol analysis is planned to be performed using available data only with no missing data replacement methods. The exception will be incomplete dates for separation of prior and concomitant treatments, as well as for separation of AEs occurred during the study and AEs occurred prior to the initiation of the study (incomplete dates will not be replaced with any data during classification).

Prior/concomitant therapy with missing or incomplete dates of start and end of the event

Table 7.2:1 - Classification algorithm for prior, concomitant and post-treatment therapies with missing or incomplete dates of start and end of the event

Start date	End date	Actions
Known	Known	To be considered as prior therapy, if the end date is < the start date of the study drug To be considered as concomitant therapy, if the end date is >= the start date of the study drug and the start date is <= the end of treatment To be considered as post-treatment therapy, if the end date is >= the start date of the study drug and the start date is > the end of treatment
	Partially missing	The end date should be replaced with the latest date possible (i.e. the last day of the month, if the day is unknown, or December 31, if the day and the month are unknown), then: To be considered as prior therapy, if the end date is < the start date of the study drug To be considered as concomitant therapy, if the end date is >= the start date of the study drug and the start date is <= the last administration date To be considered as post-treatment therapy, if the end date is >= the start date of the study drug and the start date is > the end of treatment
	Missing	The event should not be considered as prior, if the end date is missing To be considered as concomitant therapy, if the start date is <= the last administration date To be considered as post-treatment therapy, if the start date is > the end of treatment

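### Two exploratory percentages in SAP 9.3 are not limited to patients who could progress or withdraw, and the steroid-injection rule accepts route OTHER without a joint or indication check

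*SAP*

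**What the plan says.** SAP section 9.3 adds results beyond the protocol's endpoints and names their population: "This exploratory analysis will be carried out in the Full Analysis Set (FAS"). Under SAP section 6 the FAS needs one dose of Theraflex and at least one evaluable efficacy or safety parameter. It sets no condition on hypertension, diabetes, obesity or analgesic use.

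Two items matter here:

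- "The percentage of patients with no progression of arterial hypertension, diabetes mellitus and obesity at the end of observation". The three conditions share one bullet, which does not say whether they are reported jointly or one by one.
- "The percentage of patients with a complete withdrawal of analgesic treatment of pain in the target joint".

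Footnotes 3 and 5 give the source of both: "According to the “MEDICAL DATA COLLECTION AT THE END OF OBSERVATION” form". The answer options on that form are not in the documents. Neither bullet states a denominator. By contrast, the KOOS responder items in the same section are restricted, for example "in the group of patients with knee OA as assessed using the relevant KOOS subscale", and the HOOS items are restricted to hip OA in the same way. The missing-data rule in SAP section 7.2 is analysis "using available data only with no missing data replacement methods".

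For intra-articular glucocorticosteroids, footnote 8 says "Route of administration will be provided in the CM domain" and accepts the CMROUTE values OTHER or intra-articular. Footnote 9 adds an ATC filter (codes beginning H02AB). No joint or indication filter is given. The hyaluronic acid item has only an ATC footnote (M09AX), and patients given platelet-rich plasma are to be specified with the sponsor and a medical writer.

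**The concern.** A patient without diabetes has no diabetes to progress, and a patient who never took analgesics cannot withdraw from them. If such patients enter these percentages, the result partly measures how common the condition or the drug use is in the cohort. The text is loose enough that two programmers could produce very different figures from the same data.

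The study has no comparator, and these items appear under an efficacy heading as treatment-related analyses. A reader is likely to take them at face value as signs of benefit or its absence.

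The route rule raises a separate problem of classification. A glucocorticosteroid given by some unlisted non-joint route and stored as OTHER meets the written definition of an intra-articular injection.

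**Working it through.** The documents give no prevalence, progression rate or withdrawal rate, so there is no planned figure to reproduce. Every rate below is an assumption chosen to show the range.

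**No progression.** Let p be the share of FAS patients with the condition and q the share of those who do not progress.

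- Unaffected patients counted as non-progressors: 1 − p(1 − q).
- Unaffected patients in the denominator only: p × q.
- Denominator limited to affected patients: q, whatever p is.

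| p | q = 70%, counted as non-progressors | q = 70%, denominator only | q = 90%, counted as non-progressors | q = 90%, denominator only |
|---|---|---|---|---|
| 10% | 97% | 7% | 99% | 9% |
| 20% | 94% | 14% | 98% | 18% |
| 40% | 88% | 28% | 96% | 36% |
| 60% | 82% | 42% | 94% | 54% |

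For example, p = 20% and q = 70% give 1 − 0.20 × 0.30 = 0.94, or 0.20 × 0.70 = 0.14. The two codings move the figure in opposite directions from the true 70%.

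**Complete withdrawal.** Let u be the share using analgesics at start and w the share of users who stop completely. If never-users stay in the denominator, the figure is u × w. With w = 40%:

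- u = 30%: 0.30 × 0.40 = 12%
- u = 50%: 0.50 × 0.40 = 20%
- u = 80%: 0.80 × 0.40 = 32%

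Among users only, it is 40% in each case.

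**Steroid injections.** The reported rate is the true intra-articular rate plus the rate of patients counted only through a non-joint OTHER record. With a true rate of 2%:

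- a further 0.5% gives 2.5%, and 0.5/2.5 = 20% of those counted are misclassified
- a further 1% gives 3%, and 1/3 = 33% are misclassified
- a further 2% gives 4%, and 2/4 = 50% are misclassified

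**Does the available-data rule settle it?** No. It deals with values that are absent. An unaffected patient with a completed form may have a recorded value, so the rule does not by itself remove that patient.

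**The case against.** The strongest reply is that an analysis set is not a denominator. The KOOS and HOOS responder items fall under the same FAS sentence and are still confined to knee or hip patients, so in section 9.3 the FAS may only be the source population. The end-of-observation form might offer a not-applicable answer, or be completed for a condition only where it exists. Then unaffected patients would never count as non-progressors. SAP section 9.2 also reports analgesic use at start, which lets a reader put the withdrawal figure in context.

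Much of this stands, and it rules out several stronger readings that a reader might infer:

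- *That the SAP fixes the whole FAS as the denominator.* It names the set and leaves the denominator of these two items unstated.
- *That no progression is necessarily pushed towards 100%.* That holds under one coding; the other pushes it down. The form is not available to decide between them.
- *That about a fifth of patients will lack the form.* This would carry the roughly 7% loss at Visit 2, seen in the first 10% of subjects, across three intervals: 1 − 0.93³ = 19.6%. A constant rate is an assumption. An early leaver may also still have a form, since SAP section 9.2 describes an assessment up to discontinuation.
- *That the OTHER rule covers hyaluronic acid or platelet-rich plasma.* Footnote 8 is attached only to the glucocorticosteroid item.
- *That all the exploratory percentages are affected.* The KOOS and HOOS groups are stated, and all treated patients are a sensible base for the surgery, emergency-visit and injection items.

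What the reply does not do is supply the missing restriction. The authors wrote one where they wanted it, and these two items have none. The steroid rule is explicit and has no joint or indication check.

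**Conclusion.** The point holds in limited form. As written, the no-progression and complete-withdrawal percentages can include patients who cannot have the event, and the SAP does not say how those patients are handled. For an assumed true 70%, the no-progression figure could be anywhere from 82% to 97% or from 42% to 7%, depending on coding and on prevalence between 60% and 10%. The direction of the error is not established. The withdrawal figure can only be lowered, and only if never-users stay in the denominator.

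The steroid-injection count could include non-joint records. Whether it does, and by how much, depends on the number of OTHER records, which the documents do not give.

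All these are exploratory, descriptive results in an unpowered single cohort. The primary KOOS and HOOS endpoints are unaffected. The change should be made, but the main analysis does not depend on it.

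**What to change.** In SAP section 9.3, state a numerator and a denominator for these items:

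- Report no progression separately for hypertension, diabetes and obesity, each among patients with that condition ongoing at Visit 1 and a completed end-of-observation form. SAP section 8.4 already classifies diseases as ongoing or resolved.
- Report complete withdrawal among patients using analgesics at start, which SAP section 9.2 already captures.
- Show the number of patients without the form beside each percentage.
- Count a glucocorticosteroid record with route OTHER as intra-articular only when the recorded indication or a medical review supports it. Indication is collected under SAP section 8.5, and section 9.2 already uses target-joint indication categories.

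The KOOS, HOOS, surgery, emergency-visit and injection denominators need no change. The cost is some SAP wording, simple filters on collected data and a short record review. The downside is smaller denominators, hence less precise percentages, and possibly less favourable figures.
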